# 8.1.1 Screening Period

The Screening Period is defined as the three-week period prior to Week 0 (IMP administration).

Before the initiation of study-specific screening assessments, the subject must be given a complete explanation of the purpose of the study and evaluations that will be made as part of the study. Subsequently, the subject must sign and receive a copy of an Informed Consent Form that was approved by the Institutional Review Board (IRB)/Independent Ethics Committee (IEC). Once informed consent has been obtained, the eligibility of the subject to participate in this study will be determined by the Investigator on the basis of the inclusion and exclusion criteria in Section 7.4. Screening Period assessments will also be performed to determine eligibility. Only eligible subjects will be randomized to receive IMP at Week 0.

Following a discussion of participation in the clinical study and signed informed consent obtained, the following procedures will be performed to determine the subject's eligibility for this study (Table 8–1) during the Screening Period (Week -3 to Week 0):

- Informed Consent
- Interview to collect subject medical history, including but not limited to, disease history (including asthma history, number of asthma exacerbations in the previous year, hypersensitivity to aspirin or other NSAIDs), surgical history (including the number and dates of previous nasal polypectomies), recently discontinued and concomitant medications (include all background therapy for AERD).
- Demographic data
- Administer SNOT-22.
- Perform spirometry to ensure the subject has stable asthma (FEV1 ≥ 60% of predicted normal and has not experienced any exacerbation requiring treatment with ≥ 1 systemic (oral or parenteral) steroid bursts for worsening asthma and/or hospitalization or an emergency/urgent medical care visit for worsening asthma in the previous three months or are on a dose of inhaled corticosteroids > 1000 µg fluticasone or equivalent daily).
- Obtain fasting blood samples for screening clinical laboratory determinations:
  - Hematology: To include hemoglobin, hematocrit, platelet count, total white blood cell count with five-part differential count, and total red blood cell count.
  - Serum chemistry: To include creatinine, blood urea nitrogen, glucose, uric acid, total cholesterol, total protein, albumin, total bilirubin, alanine aminotransferase, aspartate aminotransferase, alkaline phosphatase, electrolytes (sodium, potassium, chloride), bicarbonate, and creatine phosphokinase.
  - o Prothrombin time (PT) and international normalized ratio (INR)
- Review entry criteria to assess eligibility with special attention to verify the following:
  - History of at least two reactions to oral aspirin or other nonselective cyclooxygenase inhibitor with features of lower airway involvement (cough, chest tightness, wheezing, dyspnea) or one reaction that was life-threatening and required

hospitalization, or diagnosis of AERD via a physician-conducted challenge to aspirin in the last five years before starting treatment

- O Use of oral or systemic steroids (e.g. prednisone or equivalent) > 20 mg daily in the last four weeks before starting treatment, daily use of long-acting antihistamines in the last two weeks before starting treatment. Subjects on 5-lipoxygenase inhibitors (e.g. zileuton) and/or leukotriene receptor antagonists (e.g. montelukast) must be on a stable dose for ≥ 30 days before starting treatment. No NSAID, anticoagulants and immunosuppressive medication use is allowed.
- o Presence of a score of at least 20 on the SNOT 22
- Perform physical examination including vital signs [blood pressure, heart rate, respiration rate, body temperature, weight (kg), height (cm)]
- Obtain pregnancy test if female of child-bearing potential (pre-menopausal female biologically capable of becoming pregnant). Confirm subject is protected by one of the following acceptable forms of effective contraception during the study:
  - Established use of oral, injected or implanted hormonal contraceptive
  - "Double barrier" methods (i.e., Double Intrauterine device with copper or intrauterine system with progestogen and barrier contraceptive [condom, diaphragm or cervical/vault caps] used with spermicide [foam, gel, film, cream or suppository])
  - Female sterilization (e.g., tubal occlusion, hysterectomy or bilateral salpingectomy)
  - Male sterilization with post-vasectomy documentation of the absence of sperm in the ejaculate; for female subjects enrolled in the study, the vasectomized male partner should be the sole partner for that subject
- Dispense subject diary, provide instructions for daily use and remind subject to bring it to the next visit.
- Schedule appointment for next visit

#### 8.1.2 Treatment Period

# Week 0 Start of Treatment Visit - Randomization

After the three-week Screening Period, subjects will come into the site for Week 0 Visit.

• Interval history, record baseline signs and symptoms, record all medication use with start date and dose and check for prohibited medications.

- Perform a limited physical exam with vital signs (blood pressure, heart rate, respiration rate, body temperature, weight)
- Administer TNSS, ACQ-7, and SNOT-22
- Obtain spirometry result and record in the electronic CRF (eCRF)
- Reconfirm eligibility based on review of Inclusion/Exclusion criteria

A subject will be considered to have failed screening if entry criteria are not met and should be discontinued.

#### If the subject meets all inclusion and does not meet any exclusion criteria:

- Subject will be randomized
- PNIFR and FeNO will be recorded
- Perform serum/urine pregnancy test (for women of childbearing potential). Confirm subject is protected by one of the following acceptable forms of effective contraception during the study:
  - Established use of oral, injected or implanted hormonal contraceptive
  - "Double barrier" methods (i.e., Double Intrauterine device with copper or intrauterine system with progestogen and barrier contraceptive [condom, diaphragm or cervical/vault caps] used with spermicide [foam, gel, film, cream or suppository])
  - Female sterilization (e.g., tubal occlusion, hysterectomy or bilateral salpingectomy)
  - Male sterilization with post-vasectomy documentation of the absence of sperm in the ejaculate; for female subjects enrolled in the study, the vasectomized male partner should be the sole partner for that subject
- Perform blood sampling (prior to administration of IMP) for clinical laboratories: hematology, chemistry, PT, and INR.

Note: Clinical laboratory testing at Week 0 Visit is limited to biomarkers in serum and plasma if screening labs were performed within three weeks of starting IMP treatment.

- Collect urine and blood samples for eicosanoid metabolites.
- Collect nasoabsorptive matrix for eicosanoid measurements.

- Conduct a smell test (UPSIT)
- Collect data from subject diary and remind subject to record daily medication usage including IMP, exacerbations, rescue medication or antibiotic usage, if applicable, twice daily TNSS (AM and PM) and to bring their diary to the next visit
- Pre-IMP Dietary Assessment
- Dispense IMP and administer IMP
- Commence AE reporting
- Schedule appointment for next visit

Treatment Period (Week 0 to Week 8): Subjects will take ifetroban or placebo daily for eight weeks. There will be a telephone encounter one week into this Treatment Period to ensure safety and confirm that baseline asthma symptoms have not worsened.

#### **Week 4 Treatment Visit**

After four weeks of treatment, subjects will return to the site for Week 4 Treatment Visit.

- Record all medication use with start date and dose and check for prohibited medications.
- Inquire about AEs/Serious Adverse Events (SAEs) and IMP tolerability
- Perform a limited physical exam with vital signs (blood pressure, heart rate, respiration rate, body temperature, weight)
- Administer TNSS, ACQ-7, and SNOT-22
- Obtain spirometry, PNIFR and FeNO
- Perform serum/urine pregnancy test (for women of childbearing potential) Confirm subject is protected by one of the following acceptable forms of effective contraception during the study:
  - Established use of oral, injected or implanted hormonal contraceptive
  - "Double barrier" methods (i.e., Double Intrauterine device with copper or intrauterine system with progestogen and barrier contraceptive [condom, diaphragm or cervical/vault caps] used with spermicide [foam, gel, film, cream or suppository])

- Female sterilization (e.g., tubal occlusion, hysterectomy or bilateral salpingectomy)
- Male sterilization with post-vasectomy documentation of the absence of sperm in the ejaculate; for female subjects enrolled in the study, the vasectomized male partner should be the sole partner for that subject
- Collect urine and blood samples for eicosanoid metabolites.
- Collect nasoabsorptive matrix for eicosanoid measurements.
- Conduct a smell test (UPSIT)
- Review subject diary for IMP compliance, content and completeness; collect data from subject diary and remind subject to continue recording daily medication usage including IMP, time of meals and doses, exacerbations, rescue medication or antibiotic usage (if applicable), twice daily TNSS (AM and PM) and to bring their diary to the next visit
- Dispense IMP and administer IMP
- Schedule appointment for next visit

#### **Week 8 End of Treatment Visit**

After four additional weeks of treatment, subjects will return to the site for Week 8 End of Treatment Visit.

- Record all medication use with start date and dose and check for prohibited medications.
- Inquire about AEs/SAEs and IMP tolerability
- Perform a limited physical exam with vital signs (blood pressure, heart rate, respiration rate, body temperature, weight)
- Administer TNSS, ACQ-7, and SNOT-22
- Obtain spirometry, PNIFR and FeNO
- Perform serum/urine pregnancy test (for women of childbearing potential). Confirm subject is protected by one of the following acceptable forms of effective contraception during the study:
  - Established use of oral, injected or implanted hormonal contraceptive

- "Double barrier" methods (i.e., Double Intrauterine device with copper or intrauterine system with progestogen and barrier contraceptive [condom, diaphragm or cervical/vault caps] used with spermicide [foam, gel, film, cream or suppository])
- Female sterilization (e.g., tubal occlusion, hysterectomy or bilateral salpingectomy)
- Male sterilization with post-vasectomy documentation of the absence of sperm in the ejaculate; for female subjects enrolled in the study, the vasectomized male partner should be the sole partner for that subject
- Perform blood sampling for clinical laboratories: hematology, chemistry, PT, and INR.
- Collect urine and blood samples for eicosanoid metabolites.
- Collect nasoabsorptive matrix for eicosanoid measurements.
- Conduct a smell test (UPSIT)
- Review subject diary for IMP compliance, content and completeness; collect data from subject diary and remind subject to continue recording daily medication usage, time of meals and doses, exacerbations, rescue medication or antibiotic usage (if applicable), twice daily TNSS (AM and PM) and to bring their diary to the next visit
- Schedule appointment for next visit

#### 8.1.3 Post-treatment Period

After two weeks post-treatment, subjects will return to the site for Week 10 Post-treatment Visit.

- Record all medication use with start date and dose and check for prohibited medications.
- Inquire about AEs/SAEs
- Perform a limited physical exam with vital signs (blood pressure, heart rate, respiration rate, body temperature, weight)
- Administer TNSS, ACQ-7, and SNOT-22
- Obtain spirometry, PNIFR and FeNO
- Perform blood sampling for clinical laboratories if abnormal at Week 8 only: hematology, chemistry, PT, and INR.

- Collect urine and blood samples for eicosanoid metabolites.
- Collect nasoabsorptive matrix for eicosanoid measurements.
- Conduct a smell test (UPSIT)
- Review subject diary for content and completeness; collect data from subject diary
- Propose the optional qualitative self-assessment of the treatment to the subject

Table 8–1 Schedule of Treatment & Events

	Screening Period	Treatment Period			Post-treatment Period	
	Visit(s)	Visit	Phone Call	Visit	Visit	Visit
	Week -3 to Week 0	Week 0	Week 1	Week 4 (± 5 days)	Week 8 (± 5 days)	Week 10 (± 5 days)
Informed Consent	X					
Inclusion/Exclusion Criteria	X					
Medical & Surgical History	X					
Subject Demography	X					
Physical Exam with vital signs	X					
Limited Physical Exam with vital signs		X		X	X	X
Spirometry (FEV1)	X	X		X	X	X
PNIFR and FeNO		X		X	X	X
Pregnancy Test (Serum/Urine) a	X	X		X	X	X
Hematology b	X	X d			X	Xe
PT, INR, Chemistry c	X	X d			X	Xe
SNOT-22, TNSS, ACQ-7	$X^{\mathrm{f}}$	X		X	X	X
Smell test (UPSIT)		X		X	X	X
Collect urine & blood for eicosanoid levels		X		X	X	X
Collect nasoabsorptive matrix for eicosanoid levels		X		X	X	X
Self-assessment of the treatment (optional)					X	
Dispense IMP		X		X		
IMP Dosing	II Ontinual Once Daily Dosing (200 mg/day)I					
Record Concomitant Medications	II					
AE/SAE Recording (if any)		II				
Dispense, review and/or collect subject diary		X		X	X	X

a) For women of childbearing potential; b) Hemoglobin, hematocrit, platelet count, total white blood cell count with five-part differential count, and total red blood cell count; c) Creatinine, blood urea nitrogen, glucose, uric acid, total cholesterol, total protein, albumin, total bilirubin, alanine aminotransferase, aspartate aminotransferase, alkaline phosphatase, electrolytes (sodium, potassium, chloride), bicarbonate, and creatine phosphokinase; d) Week 0 hematology, chemistry, PT and INR do not have to be repeated if Screening labs were performed within 3 weeks of starting IMP; e) Week 10 hematology, chemistry, PT and INR only performed for abnormal labs at Week 8; f) SNOT-22 only at Screening; All 3 questionnaires are required at subsequent visits.

ACQ-7 = Asthma Control Questionnaire; AE = adverse event; FEV1 = Forced Expiratory Volume in 1 Second; FeNO = Fractional exhaled Nitric oxide; IMP = Investigational Medicinal Product; INR = international normalized ratio; PNIFR = Peak Nasal Inspiratory Flow Rate; PT = prothrombin time; SAE = serious adverse event; SNOT = Sino-nasal Outcome Test; TNSS = Total Nasal Symptom Score; UPSIT = Smell Identification Test

# 9 SUBJECT DISCONTINUATION AND STUDY OR SITE TERMINATION

# 9.1 Subject Discontinuation

Subjects will be encouraged to complete the study; however, they may voluntarily withdraw at any time. The Investigator will provide a report in the CRF describing the reason for discontinuation. If a subject withdraws before completion, every effort should be made to complete the assessments scheduled during the final scheduled assessment.

A subject may be terminated early from the study for the following reasons:

- The subject elects to withdraw consent from all future study activities, including follow-up.
- The subject is "lost to follow-up" (i.e., no further follow-up is possible because attempts to reestablish contact with the participant have failed).
- The subject dies.
- The subject develops a medical condition or is started on new medication(s) prohibited by the study or not previously mentioned in the list of prohibited medications that, in the opinion of the investigator, may pose additional risks from participation in the study, may interfere with the subject's ability to comply with study requirements or that may impact the quality of the data obtained from the study.
- If, in the course of an asthma exacerbation, a study investigator decides to discontinue study medication (ifetroban/placebo), the subject will be withdrawn from the study.
- In addition, subjects must be withdrawn from the study if any of the following occur:
  - Any serious adverse event related to study medication (ifetroban/placebo or aspirin) or to a study procedure
  - Serious arrhythmia requiring therapy
  - $\circ$  Thrombocytopenia  $< 50 \times 10^9/L$
  - Anemia (a fall in baseline hemoglobin of 10% or more)
  - Gastrointestinal bleeding

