#### 5.5 **Risk-Benefit Assessment**

Ifetroban prevents TPr ligand binding and activation which plays a key role in the pathophysiology of AERD. Phase 2a data in AERD demonstrated a signal of efficacy for ifetroban compared to placebo with improvements seen in PNIFR and TNSS both before and during the aspirin challenge, higher provoking doses of aspirin and fewer rescue medications. While the aim of the Phase 2a study was safety, these encouraging trends provide a compelling case to further evaluate whether ifetroban will provide a benefit to subjects with AERD. This subsequent Phase 2 study aims to explore this signal in symptomatic AERD subjects in the absence of an aspirin challenge. The anticipated risks associated with the administration of oral ifetroban are well understood given the mechanism of action and its current safety database comprised of over 1,300 subjects. Based upon the current available data for ifetroban and the review of the data by an independent data monitoring committee, no important identified risks have been established. There is a potential risk based on the mechanism of action that treatment with a TPr antagonist may inhibit platelet function and thereby increase the risk of bleeding in AERD subjects. Although our Phase 2a study in subjects with a history of AERD did not demonstrate any abnormal laboratory findings or bleeding events, clinical laboratory results will be monitored for possible abnormalities related to clotting or bleeding in all study subjects.

Given the preclinical and clinical data, there is a potential benefit to study subjects randomized to the ifetroban arm to experience a reduction in the incidence and severity of respiratory reactions. If TPr antagonism does indeed provide symptom control and improve the quality of life (QoL) for subjects with AERD, it would support the use of ifetroban as a therapeutic agent. As such, the potential risk to subjects seems reasonable compared to the potential benefit.

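### No blood count is scheduled between first dose and Week 8, so the two count-based withdrawal rules cannot shorten dosing on schedule; a CBC at the existing Week 4 draw would fix this cheaply

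*Protocol*

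**What the plan says.** Section 9.1 lists events after which a subject must leave the study. Two can be established only by a blood count: platelets below 50 x 10^9/L, and "Anemia (a fall in baseline hemoglobin of 10% or more"). No confirmatory repeat is mentioned.

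Hematology in Table 8-1 and section 8.1.2:

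- **Screening and Week 0.** The Week 0 sample can be waived if the screening sample is recent enough.
- **Week 1.** A phone call only: "There will be a telephone encounter one week into this Treatment Period to ensure safety and confirm that baseline asthma symptoms have not worsened". No blood is drawn.
- **Week 4.** No hematology. Blood is taken for another purpose: "Collect urine and blood samples for eicosanoid metabolites". The second drug supply is handed out at this visit: "Dispense IMP and administer IMP". Symptoms are asked about: "Inquire about AEs/Serious Adverse Events (SAEs) and IMP tolerability".
- **Week 8, End of Treatment.** "Perform blood sampling for clinical laboratories: hematology, chemistry, PT, and INR". No drug is dispensed.
- **Week 10.** "Week 10 hematology, chemistry, PT and INR only performed for abnormal labs at Week 8".

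The schedule in SAP section 4.4 shows the same pattern, with the Week 4 hematology cell empty.

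Section 5.5 names bleeding through platelet inhibition as a potential risk of the mechanism and adds that "clinical laboratory results will be monitored for possible abnormalities related to clotting or bleeding in all study subjects".

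**The concern.** The first planned count after dosing begins arrives when dosing ends. It can document a fall in hemoglobin or platelets, but it cannot cut exposure short. Before Week 8 both rules depend on someone ordering an unscheduled test, which is unlikely in a subject who feels well.

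The gap is confined to silent falls. Symptomatic bleeding is covered by the Week 1 call, the Week 4 adverse-event inquiry and examination, and the separate gastrointestinal-bleeding trigger in section 9.1. What is at stake is avoidable dosing in a subject who already meets a mandatory withdrawal rule. The primary comparison is not affected.

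**Working it through.** **The plan's own figure.** The only related figure is the sample size, and it is not in dispute. 2 x (1.960 + 1.282)^2 x 16^2/12^2 = 37.4, which rounds up to 38 per group. Power at 38 is 90.5% by the normal formula and 89.7% by noncentral t.

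**Scheduled counts that could act during dosing.** Between the first dose and the End of Treatment visit there are none. One edge case exists: the +/- 5 day window could place the Week 8 draw on day 51, five days before day 56. That visit is itself the end of treatment, so nothing is gained.

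**Dosing days a Week 4 count could spare** (eight weeks = 56 days; Week 4 = day 28 +/- 5):

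- Nominal: 56 - 28 = 28 days.
- Week 4 window with dosing to day 56: 56 - 33 = 23 to 56 - 23 = 33 days.
- Late Week 4 visit and early Week 8 visit: 51 - 33 = 18 days.
- Dosing continued during a 7-day repeat: 28 - 7 = 21 days.

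Laboratory turnaround comes off each figure. A fall that begins after Week 4 is not helped.

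**Chance hemoglobin triggers.** The documents give no within-subject variability, so a total CV of 2-5% is assumed. Readings are taken as normal, with independent errors. The trigger is H1 <= 0.9 x H0.

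- True level as a fraction of baseline: m = 1 - fall.
- One value: P = Phi((0.9 - m)/(CV x sqrt(m^2 + 0.81))).
- Confirmed by a repeat against the same baseline: bivariate normal probability that both values trigger, with correlation 0.81/(m^2 + 0.81).

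With no true change, m = 1, z = -0.10/(CV x sqrt(1.81)) and the correlation is 0.4475:

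| CV | One value | Of 76 | Confirmed | Of 76 |
|---|---|---|---|---|
| 2% | 0.0001 | 0.01 | <0.0001 | 0.00 |
| 3% | 0.0066 | 0.50 | 0.0006 | 0.04 |
| 4% | 0.0316 | 2.40 | 0.0055 | 0.42 |
| 5% | 0.0686 | 5.21 | 0.0169 | 1.28 |

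**What the repeat costs in detection** (same formulas):

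| True fall | CV | One value | Confirmed | Loss, points |
|---|---|---|---|---|
| 10% | any | 50% | 33% | 17 |
| 12% | 4% | 65% | 50% | 15 |
| 15% | 2% | 98% | 96% | 2 |
| 15% | 3% | 91% | 85% | 6 |
| 15% | 4% | 84% | 75% | 9 |
| 15% | 5% | 79% | 68% | 11 |
| 20% | 3% | 99.7% | 99.5% | 0.3 |
| 20% | 4% | 98.1% | 96.6% | 1.5 |
| 20% | 5% | 95.2% | 91.7% | 3.5 |

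At a true 10% fall z = 0 and the correlation is 0.5, so the confirmed probability is 1/4 + arcsin(0.5)/(2 x pi) = 1/3 whatever the CV. The present schedule detects none of these falls before Week 8.

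**If the Week 4 CBC were added without a repeat.** Up to about 5 of 76 subjects could be withdrawn by chance, and section 9.1 does not replace them. If subjects lost were excluded, power by the normal formula would be about 89.3% with 3 lost and 88% with 6 lost, against 90.5% with none. In practice End of Treatment assessments are done at discontinuation (protocol 8.1) and LOCF keeps the subject in the analysis (SAP 5.1), so the loss is modest. It would be a cost of adding a count under an unconfirmed rule. The current plan does not incur it.

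**The case against.** The strongest reply is that nothing here is an error. Section 5.5 gives no frequency for laboratory monitoring, and samples at baseline, Week 8 and conditionally Week 10 meet its wording. Section 9.1 lists events that require withdrawal when they occur and does not promise to look for each on a schedule; it also lists serious arrhythmia, and Table 8-1 has no ECG. Withdrawal does more than stop dosing, because it brings at least 30 days of safety follow-up. The expected rate of silent falls is low: Phase 2a showed no abnormal laboratory findings or bleeding, the safety database exceeds 1,300 subjects, and section 7.4.2 excludes bleeding diathesis and recent anticoagulant, antiplatelet or NSAID use. A CBC also does not measure platelet function, which is the mechanism named in section 5.5.

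All of this stands and lowers the priority. It does not let the two count-based rules act on a silent fall before dosing ends.

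A reader might infer more than the documents support:

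- **That the schedule breaks the monitoring commitment in section 5.5.** No frequency is stated there, and no text ties the section 9.1 cut-offs to it. That link is inference.
- **That subjects are unprotected against bleeding.** Symptomatic bleeding has its own checks and its own trigger, and unscheduled tests remain possible.
- **That a total of subject-days saved can be quoted.** This would need a silent-fall rate, which the documents do not give, as well as full detection and no delay for the repeat.
- **That every hemoglobin fall should be confirmed first.** That would loosen the mandatory stop for symptom-prompted tests, the one route by which the rule can now act before Week 8.

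**Conclusion.** The point holds as a cheap improvement to safety monitoring. The schedule fact is certain: neither the hemoglobin rule nor the platelet rule can shorten dosing on schedule, because the first planned on-treatment count coincides with the end of treatment. For a fall present and detected at Week 4, an added CBC could spare about 28 of 56 dosing days (at most 33), or about 21 if dosing continues through a 7-day repeat.

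How often this would matter is unknown and probably seldom. The case for the repeat rests on the assumed hemoglobin CV. At 2-2.5% chance triggers are about 0.1 of 76 or fewer and the repeat adds almost nothing; at 4-5% it prevents roughly 2 to 4 chance withdrawals (2.40 - 0.42 = 1.98; 5.21 - 1.28 = 3.93). The price is weaker detection, largest for falls close to 10%. No stated statistical figure is wrong, and the current schedule causes no loss of primary-endpoint data.

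**What to change.** 1. Add a CBC to the Week 4 blood draw in Table 8-1, the Week 4 list in section 8.1.2 and the schedule in SAP section 4.4.
2. In section 9.1, for an asymptomatic subject whose scheduled Week 4 hemoglobin is down 10% or more, require a prompt repeat (for example within 7 days) before withdrawal, with the investigator free to hold dosing meanwhile.
3. Leave section 9.1 unchanged for symptom-prompted tests, for any bleeding, and for platelets below 50 x 10^9/L.

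The cost is a protocol amendment with matching schedule changes, about 76 CBCs at a draw already planned, and a few repeat draws. Repeats for chance falls at Week 4 would number between almost none and about 5 of 76 over the assumed CV range. Chance withdrawals after confirmation would number 0 to 1.3. Holding dosing during the repeat keeps the full saving for a true fall but briefly interrupts treatment in a subject whose fall was chance.
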